8.7 Subject Discontinuation/Withdrawal Criteria

Once the subject has been enrolled in the study, she/he may withdraw her/his consent to participate in the study at any time without prejudice. Participation in this clinical investigation is entirely voluntary. Likewise, there may be a reason identified by the Investigator that deems the subject no longer suitable for the study. In either case, the Investigator will contact Cheetah Medical to discuss the circumstances for discontinuation/withdrawal. Discontinuation or withdrawal may occur for any of the reasons listed below (this list is not all inclusive).

1. Subject is uncooperative with compliance of required study tests and/or medical management
2. Investigator determines that subject has developed a condition in which continued participation in the study is considered potentially harmful to the subject
3. Subject withdraws their consent
4. Adverse event which is considered intolerable by the patient, their LAR or the Principal Investigator
5. Subject has a significant protocol violation
6. Subject incorrectly enrolled in the study
7. Cheetah Medical terminates the study

8.7.1 Subjects Lost to Follow-Up

Subjects may be considered lost to follow-up for the following reasons:

- During data analysis, data indicates there is unacceptable bias in the measurements
- Data collection is interrupted prior to 72 hour data collection period of ICU stay
- Severe agitation and/or cardiopulmonary resuscitations resulted in poor quality data

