12.6 Subject Accountability and Missing Data

Subjects enrolled in this study are followed for a short time period, and missing data in this study is expected to occur at a low rate. All efforts will be used to prevent missing data. These efforts include, but are not limited to, complete site training and regular monitoring to help to minimize missing data.

Subjects without the minimum amount of monitoring [i.e. throughout first 72 hours of study enrollment,] and measurements specified in the protocol will be considered as missing in the final analysis. The impact of missing data on the study will be evaluated via sensitivity analyses if more than 5% of subjects do not have evaluable data for the primary outcome. In the final report, the number and proportion of subjects eligible for and compliant with each analysis population will be presented.

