## 7.3 METHODS FOR WITHDRAWALS, MISSING DATA, AND OUTLIERS

All reasonable efforts will be made to obtain complete data for all subjects; however, missing observations will occur due to death, loss to follow-up, withdrawal, non-adherence to the protocol, and possible non-evaluable assessments. Since this is unlikely due to the short follow-up time schedule and the consistent nature of data collection, missing data will not be imputed. However, should more than 5% of subjects be missing evaluable data for the primary endpoint, then as a sensitivity analysis to assess the impact of missing data on the primary endpoint treatment comparisons, treatment group comparisons on the primary endpoint will be performed where missing data are first imputed via multiple imputation linear regression using the FCS method in SAS. The multiple imputation model will use, as covariates in the imputation model, the demographic variables shown in the demographics table shell in Appendix A. A total of 10 complete datasets will be created for the multiple imputation and the primary endpoint treatment comparisons will be carried out within each imputed dataset; results will then be combined across imputed datasets using standard multiple imputation techniques in PROC MIANALYZE to obtain one treatment comparison p-value on the primary endpoint. Tables detailing missing data and analysis populations will be provided in the final report. Should the sensitivity analysis be required, it will also be provided in the final report.

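### Protocol 8.7.1 lets device-data problems, one of them judged during analysis, make a patient count as lost to follow-up, so recorded outcomes can be treated as missing

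*Protocol*

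**What the plan says.** Protocol 8.7.1 is permissive: "Subjects may be considered lost to follow-up for the following reasons". It then lists three:

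- A judgement made at the analysis stage: "During data analysis, data indicates there is unacceptable bias in the measurements".
- Monitoring that stops early: "Data collection is interrupted prior to 72 hour data collection period of ICU stay".
- Clinical events that spoil the recording: "Severe agitation and/or cardiopulmonary resuscitations resulted in poor quality data".

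The section does not say which measurements are meant, how much bias is unacceptable, who decides, whether that person is blind to arm and outcome, or whether the decision must precede database lock. The SAP neither repeats nor overrides it.

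Two passages bear on the consequence. Protocol 12.6 says that subjects lacking the minimum monitoring and measurements "will be considered as missing in the final analysis". SAP 7.3 says that "missing observations will occur due to death, loss to follow-up, withdrawal, non-adherence to the protocol, and possible non-evaluable assessments", and that "missing data will not be imputed" in the main analysis. Multiple imputation is added as a sensitivity analysis "should more than 5% of subjects be missing evaluable data for the primary endpoint".

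The primary endpoint (Protocol 7.3.1, SAP 4.2.1) is fluid balance at the earlier of 72 hours and ICU discharge. Protocol 9.3.3 lists fluid volume, 12-hourly urine output and 24-hourly creatinine as collected in addition to the Starling recordings.

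**The concern.** None of the three reasons means that the patient's outcome is unknown. The patient is normally still in hospital and the chart is still being kept. A poor bioimpedance signal during resuscitation or agitation does not invalidate a fluid chart or a creatinine result. The rule nevertheless attaches to the subject and not to the device reading.

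The first reason carries a further risk. It is applied once data are being analysed, in a trial where treatment is visibly different between arms, and nothing keeps the person applying it from seeing arm or outcome. The other two reasons describe events after randomisation. Resuscitation and severe agitation probably mark sicker patients.

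The interruption reason also conflicts with the endpoint. It has no exception for a patient who leaves the ICU before 72 hours, yet for that patient the endpoint is complete at ICU discharge. Protocol 12.6 and the per-protocol definition (SAP 6.4) likewise ask for 72 hours of monitoring without that exception, while the mITT definition (SAP 6.3) includes it. These passages must be reconciled.

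At stake is the primary comparison. If the label removes different kinds of patient, or different numbers, from the two arms, the difference in mean fluid balance is no longer a randomised comparison.

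**Working it through.** **Inputs from the documents.** Assumed SD 3 L, effect -2 L, 80 Starling and 40 control (SAP 5); two-sample t-test at two-sided 0.05 (SAP 9.1), which is 2.5% in the direction favouring Starling.

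**Plan's own figure.** The noncentrality is 2 / (3 × sqrt(1/80 + 1/40)) = 3.44 on 118 degrees of freedom. Power is 92.71%, against 92.7% stated. The inputs reproduce.

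**Inputs that the documents do not give (assumptions).** The fraction f of the Starling arm removed, and the excess e of the removed patients' fluid balance over the arm mean. In the base illustration nobody is removed from control and there is no true effect.

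**Formulas.**
- False difference favouring Starling: f × e / (1 - f)
- Standard error: 3 × sqrt(1/(80(1 - f)) + 1/40)
- One-sided false-positive rate: 1 - Φ(1.96 - difference / standard error)

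**f = 10% (8 of 80).** Standard error = 3 × sqrt(1/72 + 1/40) = 0.592 L.

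| Excess e (L) | False difference (L) | Difference / SE | False-positive rate |
|---|---|---|---|
| -1 | -0.11 | -0.19 | 1.6% |
| +1 | 0.11 | 0.19 | 3.8% |
| +2 | 0.22 | 0.38 | 5.7% |
| +3 | 0.33 | 0.56 | 8.1% |

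**Other fractions at e = +3 L.** For f = 5%, the difference is 0.05 × 3 / 0.95 = 0.16 L, the SE 0.586 L and the rate 4.5%. For f = 15%, the difference is 0.15 × 3 / 0.85 = 0.53 L, the SE 0.598 L and the rate 14.1%.

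**Equal removal in both arms.** With the same f and e in each arm, the shift f × e / (1 - f) is the same in both and cancels. What is left is lost precision. Random loss of 5%, 10% or 20% from both arms lowers primary power from 92.7% to 91.4%, 89.9% or 86.2%. The problem is therefore differential removal, not loss of numbers.

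**Bound for the reason applied at analysis.** A simulation of 40,000 null trials removed the four highest fluid balances of the 80 in the Starling arm. The bias was -0.31 L and the favourable false-positive rate about 9.3%. This is the worst that discretion over four patients could do, not a forecast.

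**The 5% trigger.** Four of 120 is 3.3%, so no sensitivity analysis would be required. Eight of 120 is 6.7% and twelve of 120 is 10%, so the 10% and 15% scenarios would trigger multiple imputation.

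**The case against.** Several points on the other side have force.

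- **Timing.** A reader might infer that all three reasons allow outcomes to be removed after they are seen. Only the first is tied to analysis. Interruption and agitation or resuscitation are events during the study, and the last counts only if data quality suffered. What stands is that nothing requires any of the three to be judged early or blind.
- **Meaning of measurements.** The word probably refers to haemodynamic recordings. If so, excluding the recordings would be enough; the text labels the subject.
- **Arm asymmetry.** Section 8.7.1 speaks of subjects in general, and Protocol 8.1 and 9.2 describe sensor placement without limiting it to one arm. The one-arm condition lies in the mITT and per-protocol definitions (SAP 6.3 and 6.4), where monitoring is required only of the treatment group. Differential removal is thus plausible, but 8.7.1 does not create it by itself.
- **Direction.** A reader might infer that removal must flatter Starling. The sign is not established: a patient who arrests and dies early has fewer hours to accumulate fluid, which is why the table includes a negative excess.
- **From label to removal.** No analysis population excludes patients lost to follow-up by name. The link runs through Protocol 12.6, which concerns monitoring and measurements, and SAP 7.3, which names loss to follow-up as a cause of missing observations. It is clearest for interrupted monitoring and a reading of the text for the other two.
- **Existing safeguard.** The imputation analysis covers larger removals, and its covariates may include severity scores, since SAP 8.1 lists SOFA and others under demographics. It remains a sensitivity analysis, and it would impute values that were in fact observed.

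**Conclusion.** The concern holds in this form: a discretionary rule, unblinded and without thresholds, can cause recorded fluid balance, creatinine and other outcomes to be treated as missing because of device-data problems that have no bearing on the primary endpoint. One of its three reasons is expressly applied after data are in hand.

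The size cannot be fixed from the documents. With 10% of the Starling arm alone removed and no true effect, the one-sided error lies between 1.6% and 8.1% for an excess of -1 to +3 L. That range rests on an assumed removal fraction, an assumed excess, an SD of 3 L and no removal from control; similar removal in both arms would largely cancel the bias. Small removals, such as 4 of 120, fall below the plan's own trigger for a sensitivity analysis.

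The documents do not support the stronger statement that the rule will produce a false benefit, nor that any patient was removed in this way. They show only that the text permits it.

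**What to change.** 1. Delete the three reasons from Protocol 8.7.1. Reserve lost to follow-up for subjects whose chart outcomes cannot be obtained.
2. State that poor or interrupted device data exclude only device-derived variables. Write the quality rules with thresholds, fix them before database lock, and have them applied blind to arm and outcome.
3. Amend Protocol 12.6 and SAP 6.3 and 6.4, with the matching Protocol 12.2.3 and 12.2.4, so that incomplete monitoring does not remove a patient from the efficacy analyses. All randomised subjects with charted fluid balance and creatinine should stay in the primary and secondary analyses. Without this step, deleting the reasons in 8.7.1 leaves the one-arm monitoring conditions in force.
4. Reconcile the 72-hour interruption wording with an endpoint that can end at earlier ICU discharge.

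The cost is protocol and SAP wording. No new data are needed.

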9. STUDY PROCEDURES

9.1 Baseline Assessments

After written informed consent is obtained, baseline assessments will be made to further determine the subject's eligibility for the study. Data collected will include:

- Demographics
- Age
- Medical history

- SOFA assessment
- Physical exam, limited
- Hemoglobin and blood gas (per chart review, if available)
- Serum creatinine level
- Lactate level (per chart review, if available)
- Urine sample (to be frozen for possible future testing)
- Optional plasma serum collection (two, 5ml samples to be frozen for possible future testing)
- Current medications

9.2 Enrollment Procedure

Assuming the subject meets all study eligibility criteria, the investigator, or designees, will place the Cheetah device (Starling SV) on the subject. The device will be evaluated for obtaining the optimum expected hemodynamic readings before the study is begun according to the Starling SV Instructions for Use (IFU). This is done to confirm that data collected from the monitoring devices will be evaluable. It is recommended that approximately 15-20 minutes are allowed for the device to autocalibrate and achieve a stable baseline prior to beginning any measurements at the initiation of the study.

If the Starling SV does not provide the expected hemodynamic recordings, it will be adjusted or replaced as needed until it provides the expected recordings. If it is determined that the device will not provide the expected recording, then the subject will be withdrawn from the study.

9.3 Data Collection Procedure

When the Starling SV is determined to be providing the expected waveforms and recordings, the study device data collection period will begin. Recorded information will be collected and stored by the device. After the data collection period has ended the data will be downloaded and used for analysis.

9.3.1 Hemodynamic Collection Methods

Starling SV: Following the Instructions for Use, the Starling SV device will be connected to the subject by placing four of the system's sensors on the subject's chest: left and right mid-clavicle and left and right mid-last ribs. The device will undergo 1 minute of autocalibration after which measurements will begin to be obtained. Data from the device is available as a visible read-out on the monitor screen and stored internally. At the conclusion of the data collection period, the data will be downloaded and provided to the sponsor or designee.

9.3.2 Fluid Assessment

A fluid assessment will be initiated at the following time points:

- Baseline (at study enrollment)
- At every clinical decision point for the first 72 hours of study enrollment. Examples of a clinical decision point include the decision to give additional fluid volume, or escalate vasopressors.

- MAP <65 during first 72 hours of study enrollment

A fluid assessment will be administered using a passive leg raise according to **Section 6.5**.

9.3.3 Additional Data Collection

Other data points and associated times will be collected in addition to the analysis of the continuous data from the Starling SV system. Types of data points for collection are:

- Medical history
- Medications
- Volume of treatment fluid administered
- Urine output (to be recorded every 12 hours)
- Respiratory status
- Serum Creatinine level (every 24 hours +/- 4 hours , for 72 hour monitoring period and at 30 day discharge)
- Lactate level (per chart review, if available)
- Significant clinical events not previously identified for study data collection, e.g. cardiac arrest, CPR, intubation, extubation, placement of catheters (intravenous, arterial, urinary, etc), etc.
- Changes in mechanical ventilator status parameters

9.4 Schedule of Assessments

Each subject will follow a schedule of assessments and events from which data will be collected (Table 1).

Table 1: Schedule of Assessments

Assessment/Event	Pre-Consent	Consent	Baseline	Enrollment-72 hours	72 hours-Discharge
Subject Identification	X				
Determine Eligibility	X				
Informed Consent		X			
Medical History			X	X	X
Physical Exam, limited, and lab values			X		
Urine Sample			X		
Optional plasma serum collection (two, 5ml samples to be frozen for possible future testing)			X		
Serum Creatinine			X	X	X (chart review)
Medications, specific			X	X	X
Volume resuscitation fluid			X	X	
Respiratory Status			X	X	X

Assessment/Event	Pre-Consent	Consent	Baseline	Enrollment-72 hours	72 hours-Discharge
(intubated, ventilated)					
Starling SV System			Attached	Continuous hemodynamic recordings	
Fluid Assessment				X	
Adverse events				X (+48 hours)	

10. SAFETY/DEVICE ASSESSMENT

10.1 Adverse Events

Subjects will be carefully monitored during the study for possible device related adverse events (AEs). The investigator or designee will determine AE occurrences and collect the required data. It is anticipated that the occurrence of device related adverse events will be a low number. All device related adverse events will be reviewed not only by the site investigator, but also by the sponsor's medical officer.

Serious Adverse events will be collected during the 72 hour (+ 48 hours) treatment period in the following areas: Cardiac, CNS, pulmonary, renal, and skin disorders.

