10.1.2 Serious Adverse Events

A serious adverse event (SAE) is any untoward medical occurrence that:

- Results in death
- Led to serious deterioration in the health of the subject, that either resulted in:
 - a life-threatening illness or injury, or
 - a permanent impairment of a body structure or a body function, or
 - in-patient or prolonged hospitalization, or
 - medical or surgical intervention to prevent life-threatening illness or injury or permanent impairment to a body structure or a body function,
- Led to fetal distress, fetal death or a congenital abnormality or birth defect

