10.2.2 Reporting Requirements of SAEs

All serious adverse events must be reported by the investigator by submitting the Adverse Event eCRF within 24 hours of learning of the adverse event.

The Investigator shall:

- a) Report to the IRB serious adverse events per the institutional requirements for timing and amount of support information,
- b) Supply the Sponsor (or designee), upon Sponsor's request, with any additional information related to the safety reporting of a particular event.

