### 9.2.2 NOT FOR FORMAL TESTING

#### 9.2.2.1 Incidence of Treatment Emergent Adverse Events (AE)

A Treatment Emergent Adverse Event (TEAE) is one that started or worsened in severity during or after randomized treatment was attempted. The number and percentage of patients with incidence of at least one TEAE will be summarized by treatment arm in a table. The summary will include the number and percent of subjects experiencing one or more AEs cumulatively up to 72 hours, one week, and 30 days. Though no formal hypothesis tests are planned, 95% confidence intervals for the difference in rates between the two arms at each time point will be completed and included using the normal approximation to the binomial distribution.

The analysis will be repeated for serious TEAS. In addition, the number and percentage of patients with at least one TEAEs will be presented by severity and relationship to study procedure; patients with more than one TEAE will be categorized according to the maximum severity and maximum relationship experienced.

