### 10.1 ALL TREATMENT EMERGENT ADVERSE EVENTS

The number of TEAEs and the number and percentage of patients with at least one TEAE, with at least one device-related TEAE, with at least one serious TEAE and with at least one device-related TEAE will be presented by treatment group. These summaries will be presented for TEAEs occurring from start of treatment through 72 hours, from 72 hours through Discharge, from Discharge through 30 days, and from the start of treatment through 30 days.

The number of TEAEs and the number and percentage of patients with at least one TEAE will be presented for each treatment group by MedDRA system organ class and preferred term. This analysis will be repeated for serious TEAEs (collected through 72 hours only), device-related TEAEs, and AEs leading to withdrawal from the study.

In addition, the by-treatment number and percentage of patients with at least one TEAEs will be presented by severity and relationship to study procedure within each system organ class and preferred term; patients with more than one TEAE within a given system organ class and preferred term will be categorized according to the maximum severity and maximum relationship experienced.

A listing of all adverse events will include the subject number, AE number, days since index procedure, the AE SOC and PT, the severity of AE, whether the AE is classified as serious (SAE), the relationship of the AE to the investigational device or procedure, the action taken, the outcome, and the adjudication status.

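### The organ scope and time window for collecting SAEs are stated inconsistently, and the SAP tabulates serious events well past both stated collection windows

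*Protocol*

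**What the plan says.** There is one definition of seriousness. Protocol 10.1.2 opens with "A serious adverse event (SAE) is any untoward medical occurrence that" and lists the criteria, without naming organ systems or a period. The rules on what is collected, and for how long, then differ:

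- **Protocol 10.1:** "Serious Adverse events will be collected during the 72 hour (+ 48 hours) treatment period", and only "in the following areas: Cardiac, CNS, pulmonary, renal, and skin disorders".
- **Protocol 9.4, Table 1:** the adverse-event row is marked for enrollment to 72 hours with a 48-hour extension. The column from 72 hours to discharge is empty, and no organ limit appears.
- **Protocol 10.2.2:** "All serious adverse events must be reported by the investigator by submitting the Adverse Event eCRF within 24 hours" of learning of the event. No organ limit or end date is given. Table 2 in Protocol 13.5 repeats the 24-hour duty, also without an organ limit.
- **SAP 10.1:** "This analysis will be repeated for serious TEAEs (collected through 72 hours only". No organ limit and no 48-hour extension.

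The analyses reach further. SAP 9.2.2.1 counts subjects "experiencing one or more AEs cumulatively up to 72 hours, one week, and 30 days", with 95% confidence intervals for the difference between arms, and adds: "The analysis will be repeated for serious TEAS". SAP 10.1 also summarises patients with a serious event from 72 hours to discharge, from discharge to 30 days, and over the full 30 days. Protocol 12.2.1 has adverse events reported until study exit.

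**The concern.** A table of serious events can be read only if each cell was open to being filled. Here the text leaves open whether a serious event outside the five areas is recorded at all, whether one between 72 and 120 h belongs in the data, and whether anything after 120 h is systematically sought. The SAP nevertheless produces serious-event tables by system organ class and by period to 30 days. A zero in a class or period that was not collected looks the same as a true zero.

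This matters here because the intervention changes fluid and vasopressor decisions, so harm need not stay within five organ areas. A non-fatal bowel ischaemia is an example of an event whose capture depends on the section followed. Protocol 10.2.1 requires only device-related events on the adverse-event form, so SAEs are the main record on that form of harm not attributed to the device. Failure to report SAEs as the protocol requires is itself a listed deviation (Protocol 14.2, SAP 7.4), and sites cannot be judged consistently against rules that disagree.

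**Working it through.** The plan gives no SAE rate or count, so there is no figure to reproduce. The check sets the rules side by side and compares the windows.

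**1. Windows, in hours**
- SAP 10.1, statement on collection: 72.
- Protocol 10.1 and Table 1, reading the 48 hours as an extension: 72 + 48 = 120.
- SAP 9.2.2.1, analysis: 72; one week = 7 × 24 = 168; 30 days = 30 × 24 = 720.
- Protocol 10.2.2: no end stated.

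**2. Share of the 30-day table covered by each stated window**
- 72 / 720 = 10%.
- 120 / 720 = 16.7%.

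**3. Test events under each rule**

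| Serious, non-fatal event | Protocol 10.1 | Protocol 10.2.2 as worded | SAP 10.1 statement on collection |
|---|---|---|---|
| Renal, at 40 h | collected | reportable | collected |
| Gastrointestinal, at 40 h | not collected | reportable | collected |
| Renal, at 100 h | collected | reportable | not collected |
| Gastrointestinal, at 100 h | not collected | reportable | not collected |
| Either, at day 10 (240 h) | not collected | reportable | not collected |

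Only the first row gets the same answer from all three. The second row shows the organ conflict, the third the 72 h against 120 h conflict. The last row shows the horizon conflict: both stated windows exclude the event, but the 30-day serious-event tables are laid out as if it would be present.

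**4. Consistency within the SAP**
SAP 10.1 summarises serious events after 72 hours in its first paragraph and, in its second, says they are collected only to 72 hours. SAP 9.2.2.1 extends them to 30 days. This conflict exists without reference to the protocol.

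**The case against.** The strongest reply is that Protocol 10.1 sets the scope, 10.1.2 defines seriousness, and 10.2.2 sets only a deadline, so that all SAEs in 10.2.2 means all SAEs within the scope of 10.1. A targeted SAE list may also be deliberate for a device that is already FDA cleared and CE marked. This reading is possible, and it turns the organ conflict into an ambiguity. But 10.2.2 does not say it, and the disagreement between 72 h, 120 h and 30 days remains.

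Three stronger readings are tempting and are not supported:

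- **That serious harm in general, including death, goes uncounted.** Deaths are reported to the sponsor within 24 hours (Protocol Table 2), analysed by arm with Kaplan-Meier curves (SAP 9.2.2.3) and listed (SAP 10.3). MACE, renal replacement therapy, ventilator use, vasopressor hours and creatinine have their own analyses. Protocol 9.3.3 also collects significant clinical events not otherwise identified. The gap is mainly non-fatal, non-MACE events.
- **That a stated share of SAEs is lost.** The 48 hours beyond 72 are 40% of the 120-hour window (48 / 120), but that is a share of hours, not of events. The documents give neither SAE rates nor their mix by organ, so any percentage would be an assumption.
- **That the comparison between arms is shown to be biased.** Uneven reporting between sites does not by itself favour an arm, because patients are randomised. Bias would need reporting that depends on the arm. No blinding is described, so that is possible, but nothing shows it. Common protocol training (Protocol 11.2.1) and monitoring work against uneven practice, and the case report forms, which might show what was captured, are not available here.

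Nor does the SAP text order events at 72 to 120 h to be discarded. Its parenthesis describes collection, and its other tables have room for those events.

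**Conclusion.** The inconsistency is real and lies in the current text of both documents. It has three parts. Organ scope is unclear between Protocol 10.1 and 10.2.2. The collection window is 120 h in the protocol and 72 h in SAP 10.1. The analysis horizon of 30 days exceeds both, covering 720 h of which 10% or 16.7% falls inside a stated collection window.

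The consequence is limited but worth correcting. Non-fatal, non-MACE serious events outside the five areas may be missed or captured unevenly. Events from 72 to 120 h are collected under the protocol but do not exist according to SAP 10.1. Later periods and uncollected organ classes could be taken as absence of harm. The loss in events cannot be sized from the documents.

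The conclusion assumes that the 48 hours extend the window. The organ part also depends on taking 10.2.2 as worded; the window and horizon parts do not.

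**What to change.** 1. **SAP 10.1 and 9.2.2.1.** Replace the 72-hour statement in SAP 10.1 with the protocol window of 72 h + 48 h. Limit the serious-event tables in both sections to that window, or mark later periods as not systematically collected. Changing the parenthesis alone would leave the one-week and 30-day outputs unresolved.
2. **Protocol 10.1 and 10.2.2.** State one organ scope for all sites and both arms. Preferably this is every SAE that meets 10.1.2, with the five areas kept as events of special interest. If the five-area limit was intended, say so in 10.2.2 and mark other organ classes in the SAP tables as not collected rather than zero.
3. **Protocol 12.2.1.** Align the adverse-event reporting period with the same window.

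The cost is a short protocol clarification with IRB notification or approval, SAP wording, and modestly more SAE forms at sites that applied the five-area limit. If such sites have already enrolled, earlier events outside the five areas would need a look-back or a note that they were not collected.
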